8.6 Audits and inspections

Authorised representatives of AstraZeneca, a regulatory authority, or an Ethics Committee may perform audits or inspections at the centre, including source data verification. The purpose of an audit or inspection is to systematically and independently examine all study-related activities and documents, to determine whether these activities were conducted, and data were recorded, analysed, and accurately reported according to the protocol, GCP, guidelines of the ICH, and any applicable regulatory requirements. The investigator will contact AstraZeneca immediately if contacted by a regulatory agency about an inspection at the centre.

For Japan, add the below paragraph

All study data may undergo a reliability review and onsite-GCP inspection by the regulatory authorities.

9. STUDY MANAGEMENT BY ASTRAZENECA

9.1 Pre-study activities

Before the first subject is entered into the study, it is necessary for a representative of AstraZeneca to visit the investigational study site to:

- Determine the adequacy of the facilities
- Determine availability of appropriate subjects for the study
- Discuss with the investigator(s) (and other personnel involved with the study) their responsibilities with regard to protocol adherence, and the responsibilities of AstraZeneca or its representatives. This will be documented in a Clinical Study Agreement between AstraZeneca and the investigator.

9.2 Training of study site personnel

Before the first subject is entered into the study, an AstraZeneca representative will review and discuss the requirements of the Clinical Study Protocol and related documents with the investigational staff and also train them in any study specific procedures and WBDC system(s) utilised.

The Principal Investigator will ensure that appropriate training relevant to the study is given to all of these staff, and that any new information relevant to the performance of this study is forwarded to the staff involved.

The Principal Investigator will maintain a record of all individuals involved in the study (medical, nursing and other staff).

Laboratory technicians who will perform the optical aggregometry at each centre will receive training in the aggregometry method used in this study and complete a pre-study aggregometry exercise prior to the recruitment of subjects. The training log should be recorded and kept in ISF. An aggregometry manual will provide guidance on all aspects of aggregometry in the study.

9.3 Monitoring of the study

During the study, an AstraZeneca representative will have regular contacts with the study site, including visits to:

- Provide information and support to the investigator(s)
- Confirm that facilities remain acceptable
- Confirm that the investigational team is adhering to the protocol, that data are being accurately and timely recorded in the eCRFs, that biological samples are handled in accordance with the Laboratory Manual and that study drug accountability checks are being performed
- Perform source data verification (a comparison of the data in the eCRFs with the subject's medical records at the hospital or practice, and other records relevant to the study) including verification of informed consent of participating subjects. This will require direct access to all original records for each subject (eg, clinic charts)

- Ensure withdrawal of informed consent to the use of the subject's biological samples is reported and biological samples are identified and disposed of/destroyed accordingly, and the action is documented, and reported to the subject.

The AstraZeneca representative will be available between visits if the investigator(s) or other staff at the centre needs information and advice about the study conduct.

9.3.1 Source data

Refer to the Clinical Study Agreement for location of source data.

For Japan, replace the above paragraph with the paragraph below

Source data are any data generated as a result of the subject's inclusion in the study (including run-in and/or follow up related to the study) and includes all related medical examinations and other records. Original data recorded on the eCRFs and regarded as source data are stated in Clinical Study Agreement.

For Japan, add the below section

9.3.2 Direct access to source data in Japan

The Head of the institution and the Principal Investigator/sub-investigator will cooperate for monitoring and audit by AstraZeneca, and accept inspection by the IRB or regulatory authorities. All study documents such as raw data will be open for direct access to source data at the request of the monitor and the auditor of AstraZeneca, the IRB, or regulatory authorities.

The monitor(s) will verify data from the eCRFs against source data before collecting the eCRFs to ensure accuracy and completeness of documentation, and assure that the Principal Investigator/sub-investigator has submitted the eCRFs to AstraZeneca. If the investigator wishes to amend the collected eCRFs, the monitor will ensure that the Principal Investigator/sub-investigator has documented the amendment in writing (signed and dated) and provided this to AstraZeneca.

9.4 Study agreements

The Principal Investigator at each/the centre should comply with all the terms, conditions, and obligations of the Clinical Study Agreement, or equivalent, for this study. In the event of any inconsistency between this Clinical Study Protocol and the Clinical Study Agreement, the terms of Clinical Study Protocol shall prevail with respect to the conduct of the study and the treatment of subjects and in all other respects, not relating to study conduct or treatment of subjects, the terms of the Clinical Study Agreement shall prevail.

Agreements between AstraZeneca and the Principal Investigator should be in place before any study-related procedures can take place, or subjects are enrolled.

9.4.1 Archiving of study documents

The Investigator follows the principles outlined in the Clinical Study Agreement (CSA).

For Japan, replace the above paragraph with the paragraph below

(i) Study files.

AstraZeneca will provide the Principal Investigator with a file in which to organise and retain all study-related documents. All study documents (including letters from AstraZeneca) should be retained in this file by the Principal Investigator. The monitor will regularly check the file to ensure that all relevant documents are retained. The contents of the file may be audited/inspected by AstraZeneca's auditor, regulatory authorities, or IRB.

(ii) Period of record retention.

The study site (and the Principal Investigator) will retain the essential documents specified in the ICH GCP (eg, source document such as medical records, contract, signed consent form). Essential documents should be retained at the study site for at least 15 years following completion of the study, or per regulatory obligations if longer, and thereafter destroyed only after agreement with AstraZeneca. However this is not always applied to those that are not preservable such as blood samples. In the event of any inconsistency between the above-mentioned contents and the contract with the study site, the contract shall prevail. These documents should be retained for a longer period however if needed by AstraZeneca, and the specific period and method of retention will be separately discussed between the study site and AstraZeneca. AstraZeneca should notify the head of the study site in writing when the study related records are no longer needed. The records should be managed by a responsible person appointed by the head of the study site.

For Japan, add the below section

9.4.2 Deviation from the clinical study protocol in Japan

The investigator(s) must not deviate from or make any changes to the protocol without documented agreement between the principal investigator and AstraZeneca K.K. or the IRB approval based on its deliberations. However, this shall not apply to cases where the deviation or change is necessary to avoid an immediate hazard to the patients or for other compelling medical reasons, or where the changes involve only logistical or administrative aspects of the clinical trial (e.g. changes to the organisation/structure of the sponsor, the name/department name of the medical institution, the address or phone number of the medical institution or the sponsor, the job title of the investigator, and monitors).

The investigator(s) should document any deviation from the protocol regardless of their reasons. Only when the protocol was not followed in order to avoid an immediate hazard to the patients or for other medically compelling reason, the investigator should prepare and submit the records explaining the reasons thereof to the sponsor, and retain a copy of the records.

The investigator(s) may deviate from or make a change to the protocol without documented agreement between the principal investigator and AstraZeneca K.K. or the IRB approval, only in the event of a medical emergency, e.g. it is only way to avoid an immediate hazard to the patients. In such case, the principal investigator must notify details of the deviation or change, the reason, and a proposed revision in the protocol if required, to AstraZeneca K.K. and the head of the study site and IRB via the head of the study site as soon as possible, in order to obtain their approval. A certificate of approval by the head of the study site as well as AstraZeneca K.K. should be obtained via the head of the study site.

9.5 Study timetable and end of study

The end of the study is defined as ‘the last visit of the last subject undergoing the study’.

The study is expected to start in 1st Quarter 2010 and to end by 2nd Quarter 2011.

The study may be terminated at individual centres if the study procedures are not being performed according to GCP, or if recruitment is slow. AstraZeneca may also terminate the entire study prematurely if concerns for safety arise within this study or in any other study with AZD6140.

For Japan, add the below section

Planned duration of the study:

Study period: February 2010 - April 2011

Registration period: April 2010 – February 2011

Discontinuation or suspension of the whole study programme

If AstraZeneca decides to prematurely terminate or suspend the study, the Principal Investigator, the head of the institution, and regulatory authorities should receive written notification of the reasons for the premature termination or suspension.

The Principal Investigator/sub-investigator will immediately notify the decision to the subjects, give appropriate medical treatment; take necessary measures, and record treatment or measures provided on the source documents.

Completion of the study

Upon terminating the study, the Principal Investigator will report in writing the completion of the study as well as the summary of the results to the head of the study site in accordance with the institution's rules. The head of the study site, who is informed of the termination by the investigator, will provide a written notification of the results to the IRB and AstraZeneca.

10. DATA MANAGEMENT BY AS COGNIZANT DMC

Data will be entered in WBDC system at the study site. Trained study personnel will be responsible for entering data on the observations, tests and assessments specified in the protocol into the WBDC system and according to the eCRF Instructions. The eCRF Instructions will also guide the study site in performing data entry. Data entered in the WBDC system will be immediately saved to a central database and changes tracked to provide an audit trail. Site personnel will enter the data in the eCRFs. The data will then be Source Data Verified (SDV), reviewed/ queried and updated as needed. The principal investigator will then sign the eCRF electronically. Clean file occurs when all data have been declared clean and signed by the investigator. The data will be frozen and then locked to prevent further editing. A copy of the eCRF will be archived at the study site when the study has been locked.

Medical coding for AEs and medical/surgical history is done using the most current version of medical dictionary of regulatory activities (MedDRA), and Medical coding for medication is done using AstraZeneca Drug Dictionary.

Data Management determines the format of the data to be received from external vendors and coordinates the flow of data to an external environment or clinical database (if applicable). Data Management will ensure that the data collection tool (IWRS) will be tested / validated as needed. External data reconciliation will be done with the clinical database as applicable.

SAE Reconciliation Reports are produced and reconciled with Patient Safety database and/or the Investigational Site.

11. EVALUATION AND CALCULATION OF VARIABLES BY ASTRAZENECA

11.1 Calculation or derivation of efficacy variable(s) - Not applicable.

11.2 Calculation or derivation of safety variable(s)

Following variables will be calculated:

- Bleeding events (to be adjudicated using PLATO criteria)
 - Major, Minor, and Minimal bleeding events.
- Bleeding events (to be adjudicated using DISPERSE criteria)
 - Major and Minor bleeding events.
- AEs, laboratory values, physical examination, 12-lead ECG, and vital signs, Holter ECG.

11.2.1 Other significant adverse events (OAE)

During the evaluation of the AE data, an AstraZeneca medically qualified expert will review the list of AEs that were not reported as SAEs and DAEs. Based on the expert's judgement, significant AE of particular clinical importance may, after consultation with the Global Patient Safety Physician, be considered OAEs and reported as such in the CSR. A similar review of laboratory/vital signs and ECG data will be performed for identification of OAEs.

Examples of these are marked haematological and other laboratory abnormalities, and certain events that lead to intervention (other than those already classified as serious), dose reduction or significant additional treatment.

11.3 Calculation or derivation of patient reported outcome variables - Not applicable

11.4 Calculation or derivation of pharmacokinetic variables

The PK analyses will be performed at AstraZeneca R&D. The actual sampling times will be used in the PK calculations. PK parameters will be determined using standard non-compartmental methods. The following PK parameters will be determined:

Maximum plasma concentration (C_{\max} and $C_{ss,\max}$), time to C_{\max} or $C_{ss,\max}$ (t_{\max} and $t_{ss,\max}$, respectively), minimum plasma concentration (C_{\min} and $C_{ss,\min}$), average plasma concentration (C_{av} and $C_{ss,av}$), half-life ($t_{1/2}$), area under the plasma concentration-time curve from zero to

dosing interval (AUC_{τ}), and accumulation ratio (R_{ac}) at Visit 2 and 5 for AZD6140 and AR-C124910XX. Oral clearance (CL/F) will be calculated at steady-state.

11.5 Calculation or derivation of pharmacodynamic variable(s)

Maximum and final extent IPA from pre-dose baseline at Visit 2 will be calculated at all subsequent timepoints using the following formula for ADP-induced platelet aggregation:

$$\text{Percentage Inhibition} = 100\% \times (PAs - PA) / (PAs)$$

PA is the mean response at the given post dose time point and PAs is the mean response at pre dose baseline. Percentage inhibition will be restricted to the closed interval [0,100]; any data falling outside this range will be truncated to the appropriate limit.

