1.3 Rationale for conducting this study

Data from Phase I studies in human volunteers demonstrate acceptable tolerability of AZD6140 over an orally administered dose range of up to 900mg and have confirmed a positive relationship between plasma concentration of AZD6140 and the degree of IPA, with substantial (over 80%) IPA achievable in all volunteers studied to date.

The Phase IIA study ([DISPERSE/D5130C00008](#)) investigated the pharmacodynamics (PDs), pharmacokinetics (PKs), safety and tolerability of AZD6140 in the total daily dose range 100 to 400 mg during 28 days of treatment in 200 patients with stable atherosclerotic vascular disease. The 50 mg twice daily dose of AZD6140 conferred a similar degree of IPA as clopidogrel 75 mg once daily during maintenance treatment but with a much faster onset with a maximal effect reached with AZD6140 already within 2 hours while not until after 24 hours with clopidogrel. The AZD6140 100 mg and 200 mg twice daily as well as 400 mg once daily resulted in a clearly higher percentage of IPA (over 20% absolute difference with all doses) and still with the maximal effect reached with AZD6140 already within the initial 2 hours after the first dose but not until after 24 hours with clopidogrel. After the initial dose there was a 10-15% higher degree of platelet inhibition with the 400 mg dose compared to the 100 and 200mg doses. However, during maintenance treatment there was no significant difference in platelet inhibition between the 100 mg, 200 mg twice daily or 400mg once daily. The pattern of IPA was the same using either final or maximal extent for ADP-induced platelet aggregation.

Based on this data doses of 100 mg and 200 mg twice daily were considered promising for further evaluation. A new tablet formulation of AZD6140 was subsequently made available in tablet strengths of 90 and 180 mg (equivalent to 100 and 200 mg of the original formulation due to improved relative bioavailability of the new formulation).

The Phase IIB study ([DISPERSE 2/D5130C00002](#)) examined the longer-term (up to 12 weeks) safety and PDs of AZD6140 in patients with non-ST elevation ACS. In total, 990 patients were randomised into three groups: AZD6140 90 mg or 180 mg twice daily or clopidogrel 75mg once daily. Half of the AZD6140 patients received a loading dose of

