12.3 Determination of sample size

The sample size is not based on formal statistical tests. As a measure of study precision, with 34 Japanese patients per group, the expected width of the 2-sided 95% confidence interval of the difference between 90mg and 45mg dose groups in IPA is approximately $\pm 12\%$, assuming the SD for the final IPA of 25% based on DISPERSE.

In order to obtain PK and PD data in non-Japanese Asian patients and to make exploratory comparison between Japanese and non-Japanese Asian, 7 non-Japanese Asian patients per group will be included. Based on DISPERSE, the difference between the higher dose (90mg) and lower dose (45mg) in final IPA at 12 hours post-dose at Week 4 was predicted to be at least 12%. With 7 non-Japanese Asian patients per group, $P(D_{NJP} > 0)$, where D_{NJP} is estimate of difference between 90mg and 45mg dose groups in IPA for non-Japanese Asian is more than 0.8. Therefore, 7 non-Japanese Asian patients per group is considered sufficient to obtain consistent result in terms of point estimates.

Assuming that there are approximately 10% premature discontinuations due to informed consent withdrawal and/or AE, 45 patients per group to be randomized in total.

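### Flooring every IPA value at 0, with no untruncated version, biases the Day 0 clopidogrel mean upward and probably understates the early contrast with AZD6140

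*Protocol*

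**What the plan says.** - **Derivation (Protocol 11.5).** Maximum and final extent IPA are calculated at every time point after the Visit 2 baseline as 100% × (PAs − PA)/PAs, where "PA is the mean response at the given post dose time point and PAs is the mean response at pre dose baseline". Then: "Percentage inhibition will be restricted to the closed interval [0,100]; any data falling outside this range will be truncated to the appropriate limit". This is the only IPA variable defined.
- **Use (12.2.1).** All PD variables are summarised at each time point by N, mean, SD, median, minimum and maximum, with mean and individual plots. ANOVA is planned only for final extent IPA on Day 28, at 2 to 24 h. Day 0 is descriptive.
- **Sampling (Table 2).** Day 0 post-dose samples are at 1, 2, 4, 8 and 12 h.
- **Onset (1.3).** In DISPERSE the lower dose had its "maximal effect reached with AZD6140 already within 2 hours while not until after 24 hours with clopidogrel". Section 3.2 rules out a loading dose in every arm.
- **Scatter (12.3).** Precision is calculated "assuming the SD for the final IPA of 25% based on DISPERSE". The section does not say whether that SD was measured before or after truncation, or whether it applies on Day 0.

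**The concern.** IPA is a ratio to a baseline that is itself measured with error. With no true effect, about half the patients will show post-dose aggregation above baseline, and so a negative IPA. The rule turns those values into 0 and leaves the positive errors alone, so random scatter around zero becomes apparent inhibition. Sample size does not reduce this.

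The arm and period most exposed are clopidogrel on Day 0, where sampling stops at 12 h and the maximal effect is expected only after 24 h. AZD6140 is expected to be near its maximum by 2 h, well away from the floor. What is at stake is the early contrast between the drugs in the mean table and mean plot. Secondary objective 9 compares AZD6140 with clopidogrel on IPA at each assessment point. The planned minimum cannot fall below 0, so a reader cannot see how much scatter was removed.

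**Working it through.** **The plan's own figures (12.3).** The inputs are SD 25, 34 Japanese or 7 non-Japanese Asian patients per group, and a predicted difference of 12 points.
- Half-width of the 95% interval: 1.96 × 25 × √(2/34) = 11.88, or 12.11 with a t quantile on 66 df. The plan says about ±12, so it is reproduced.
- "With 7 non-Japanese Asian patients per group", the probability of a positive estimated difference is Φ(12 / (25 × √(2/7))) = Φ(0.898) = 0.815. The plan says more than 0.8, so it is reproduced.

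Neither calculation contains a truncation term, so an added untruncated analysis leaves both unchanged.

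**Which limit acts.** From the 11.5 formula, IPA is below 0 whenever PA exceeds PAs, which is ordinary. It is above 100 only if PA is negative. The lower limit is active and the upper one nearly inactive.

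**Effect of the floor on a mean.** Assume normal scatter with true mean m and SD s, clipped at 0:

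E = m·Φ(m/s) + s·φ(m/s), and bias = E − m.

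At m = 0 this is 0.399 × s. Example with m = 10 and s = 25: 10 × 0.6554 + 25 × 0.3683 = 15.76, a bias of 5.76.

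Bias in points, over assumed Day 0 values:

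| True mean | SD 5 | SD 10 | SD 15 | SD 25 |
|---|---|---|---|---|
| 0 | 1.99 | 3.99 | 5.98 | 9.97 |
| 5 | 0.42 | 1.98 | 3.81 | 7.67 |
| 10 | 0.04 | 0.83 | 2.27 | 5.76 |
| 20 | 0.00 | 0.08 | 0.64 | 3.00 |

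**Check on the aggregation scale.** A simulation kept PA at or above 0, with assumed baseline aggregation 60 (SD 10), measurement SD 5 on each reading, and true inhibition varying between patients with SD 5 points.
- True mean inhibition 0: half the values were negative. Mean IPA was −0.78 untruncated and 4.92 truncated. The median was 0.0 both ways.
- True mean inhibition 10%: the mean was 9.29 untruncated and 11.23 truncated. The median was 9.99 both ways.
- The upper limit changed nothing beyond rounding.

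**Day 28, 90 mg minus 45 mg.** The true difference is 12, SD 25 in both arms, lower limit only. Means by arm are not given, so the 45 mg mean is varied.

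| 45 mg mean | 90 mg mean | Reported difference | Loss |
|---|---|---|---|
| 20 | 32 | 10.18 | 1.82 |
| 30 | 42 | 11.08 | 0.92 |
| 40 | 52 | 11.59 | 0.41 |
| 50 | 62 | 11.84 | 0.16 |
| 60 | 72 | 11.95 | 0.05 |

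With SD 15 the loss at a 45 mg mean of 20 is 12 − 11.45 = 0.55. The 24 h reading is the likeliest place for a low 45 mg mean, because the Visit 5 evening dose is omitted (3.1) and the half-life is about 12 h (13.1).

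**The case against.** **The case for leaving the rule alone.** Day 0 enters no model. Medians and individual plots are planned, and bunching at 0 would show in them. The SD of 25 was used to size the AZD6140 dose comparison. With no true effect, only measurement and within-patient scatter remain, and PA is already a mean response, so 2 to 4 points is more plausible than 10. The protocol says when clopidogrel reaches its maximum; it does not say that the effect before 12 h is nil. The study mirrors DISPERSE, so a bounded scale may be needed for the overlay. The SAP, not available for this check, could add an untruncated summary.

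Most of this stands, and it limits the size. It does not remove the bias in the Day 0 mean and mean plot. The protocol does not say whether DISPERSE truncated, and the truncated version can be kept for the overlay in any case.

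**Stronger readings that a reader might infer, and why they fail:**
- *The rule compresses both ends of the scale.* By the formula, a value above 100 needs negative aggregation, and nothing in the protocol suggests this is recorded.
- *The primary dose difference is materially understated.* At a 45 mg mean of 40 or more, the loss is about 0.4 point or less, against a half-width of about 12.
- *Truncation can only shrink differences.* That fails with unequal SDs. With the floor alone, true means of 0 (SD 5) and 5 (SD 25) are reported as 1.99 and 12.67, so a difference of 5 becomes 10.68. Section 1.4 says IPA varies less on AZD6140 than on clopidogrel, so equal SDs cannot be assumed.
- *The sigmoid Emax fits inherit the clopidogrel bias.* Section 7.2.1 has PK assayed only in patients on AZD6140, so clopidogrel values cannot enter those fits.

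**Conclusion.** The point holds for means where true IPA is near zero, chiefly clopidogrel on Day 0. There the reported mean is too high by about 2 to 4 points at a true mean of 0 if the SD is 5 to 10, and by up to 10 points if the SD is 25. At a true mean of 10 with SD 5 to 10 the bias is under 1 point. The early AZD6140 versus clopidogrel contrast is therefore likely to be understated in the mean table and plot. The figures rest on normal scatter and on assumed Day 0 means and SDs, and the DISPERSE SD of 25 may itself be on the truncated scale. Medians are unaffected unless the untruncated median is below 0.

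For the Day 28 dose difference, the most that can be said is slight attenuation if the 45 mg mean is low: about 1.8 of 12 points at a mean of 20, assuming SD 25 in both arms. The primary objective is not threatened. This is a cheap improvement to the reporting of a biased mean.

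**What to change.** Amend Section 11.5 to derive IPA without truncation in addition to the truncated value. Then:
- report untruncated means at all time points, and the Day 28 ANOVA on untruncated IPA, beside the truncated results;
- keep the truncated version for the visual overlay with DISPERSE;
- give the number of values cut per arm and time point.

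The cost is one derived variable, a few extra tables, and some negative IPA values in listings that will need a line of explanation. Sample size, visits and data collection do not change.
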